8.2 AEs, SAEs and SUSARs

8.2.1 Adverse events (AEs)

An adverse event is any untoward medical occurrence in a patient administered a medicinal product and which does not necessarily have to have a causal relationship with this treatment. An adverse event can therefore be any unfavorable and unintended sign (for example, an abnormal laboratory finding), symptom, or disease temporally associated with the use of a medicinal product, whether or not considered related to this medicinal product. (ICH E2D)

8.2.2 Serious adverse events (SAEs)

A serious adverse event is any untoward medical occurrence or effect that at any dose:

- results in death;
- is life threatening (defined as an event in which the subject was at risk of death at the time of the event; it does not refer to an event which hypothetically might have caused death if it were more severe);
- requires hospitalisation or prolongation of existing inpatients' hospitalisation;
- results in persistent or significant disability or incapacity;
- is a congenital anomaly or birth defect;
- is an important medical event (defined as a medical event(s) that may not be immediately life-threatening or result in death or hospitalization but, based upon appropriate medical and scientific judgment, may jeopardize the subject or may require intervention [eg, medical, surgical] to prevent one of the other serious outcomes listed in the definition above.) Examples of such events include, but are not limited to, intensive treatment in an emergency room or at home for allergic bronchospasm; blood dyscrasias or convulsions that do not result in hospitalization.)

Per Health Canada requirement, sites in Canada will collect and record all Adverse Events in the eCRF. For Netherlands and Malaysia sites AEs should be recorded in the eCRF only if it qualifies as:

- An SAE
- If the AE is the reason for permanent discontinuation from investigational product (DAE), if the AE leading to Investigational Product interruption or dose reduction
- An AE of interest

- Urinary Tract Infection or Genital Infections
- Potential DKAs
- Volume depletion
- Fractures
- Major hypoglycaemic events
- Acute kidney injury
- Amputation or related events

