2. OBJECTIVES

Primary Objective:

- To assess the change from baseline in 24-hr proteinuria with dapagliflozin for six weeks relative to placebo treatment in patients with non-diabetic kidney disease and proteinuria > 500 mg/day on stable ACEi or ARB treatment.

Secondary Objectives

- To assess the effect of dapagliflozin 10 mg/d compared to placebo on Glomerular Filtration Rate (GFR) using iothexol clearance
- To assess the effect of dapagliflozin 10 mg/d compared to placebo on systolic/diastolic blood pressure
- To assess the effect of dapagliflozin 10 mg/d compared to placebo on body weight
- To assess the effect of dapagliflozin 10 mg/d compared to placebo on selected neurohormones/biomarkers:
 - Hormones of the RAAS (plasma and urine)
 - Natriuretic peptides
 - Urinary adenosine
 - Co-peptin
 - Immunoglobulin G (plasma and urine)
- To characterize the safety of dapagliflozin vs. placebo by determining the number of hypoglycemia episodes between groups and serious adverse events.

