7.1.3 Other study parameters (if applicable)

- Number of hypoglycaemic episodes
- Serious Adverse Events
- Drug related adverse events (causality to investigational product assessed by research physician).

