8.2.3 Adverse events of interest

Urinary tract infection or genital infections

All potential events of urinary tract infection or genital infections will be recorded in the eCRF.

Diabetic ketoacidosis (DKA)

All potential events of DKA will be recorded in the eCRF.

Volume depletion

Events of volume depletion (eg, dehydration, hypovolemia, or hypotension) will be collected on the eCRF as AEs.

Fractures

All fractures will be recorded in the eCRF as AEs.

Major hypoglycaemic event

A major hypoglycaemic event is defined as an event that requires assistance of another person to actively administer carbohydrates, glucagon, or take other corrective actions. Plasma glucose concentrations may not be available during an event, but neurological recovery following the corrective actions is considered sufficient evidence that the event was induced by a low plasma glucose concentration. Major hypoglycaemic episodes will be recorded in the eCRF as an AE.

Acute Kidney Injury

Acute kidney injury is defined as an increase of 40% in serum creatinine from the previous visit or hospitalization due to acute kidney injury. All acute kidney injury events will be recorded as an AE.

Amputation and related events:

Amputations and related events will be recorded in the eCRF. Information on the actual amputations will be captured as an AE.

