2.2. Secondary Objectives

- To assess the effect of dapagliflozin 10 mg/d compared to placebo on Glomerular Filtration Rate (GFR) using iohexol clearance.
- To assess the effect of dapagliflozin 10 mg/d compared to placebo on systolic/diastolic blood pressure
- To assess the effect of dapagliflozin 10 mg/d compared to placebo on body weight
- To assess the effect of dapagliflozin 10 mg/d on selected neurohormones/biomarkers:
 - Hormones of the RAAS (plasma and urine)
 - Natriuretic peptides
 - Urinary adenosine
 - Co-peptin
 - Immunoglobulin G (plasma and urine)
- To characterize the safety of dapagliflozin vs. placebo by determining the number of hypoglycemic episodes between groups, and serious adverse events.

3. Study design

Randomized placebo controlled double blind cross-over trial. Eligible participants will be randomly assigned to one of the two treatment orders: placebo-dapagliflozin *or* dapagliflozin-placebo. Each treatment period lasts 6 weeks followed by a 6 week wash-out period to avoid cross-over effects. Patients will have their study visit in the morning in fasted condition.

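### Hypoglycaemic episodes are a safety endpoint with no severity limit, but Dutch and Malaysian sites enter mainly major ones in the eCRF, so pooled rates of milder episodes would be too low

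*Protocol*

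**What the plan says.** **The endpoint.** Protocol section 2 sets out to characterise safety "by determining the number of hypoglycemia episodes between groups and serious adverse events". The protocol Summary states the same objective, and SAP section 2.2 repeats it: "determining the number of hypoglycemic episodes between groups, and serious adverse events". Protocol section 7.1.3 lists "Number of hypoglycaemic episodes" among the other study parameters. None of the four places restricts the count to major episodes.

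**The recording rule.** Protocol section 8.2.2 sets two rules. Under a Health Canada requirement, "sites in Canada will collect and record all Adverse Events in the eCRF". For the other two countries, "For Netherlands and Malaysia sites AEs should be recorded in the eCRF only if it qualifies as" a serious AE, an AE that changes dosing, or an event of interest. The dosing item covers permanent discontinuation and also reads "if the AE leading to Investigational Product interruption or dose reduction". The events of interest include hypoglycaemia only in its major form. Section 8.2.3 defines that as an event in which another person has to help, and adds: "Major hypoglycaemic episodes will be recorded in the eCRF as an AE". The protocol gives no definition of a non-major episode.

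**The analysis.** SAP section 6 is two sentences long. One plans counts and percentages by treatment arm, and the other splits serious AEs by fatal or non-fatal status. The section does not mention the difference between countries, and SAP section 7 has no AE table shell.

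**The concern.** Hypoglycaemia is one of the two components named in the safety objective, and the count is collected under two rules. If the protocol is followed exactly, a mild episode enters the database from Toronto but normally not from Groningen or Kuala Lumpur. Dividing the pooled count by all patients gives a figure that is neither the rate of all episodes nor the rate of major episodes.

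At stake are the absolute frequency on each treatment, the absolute difference between treatments, and the meaning of a low or zero count. A reader would take a zero to rest on every patient when, for milder episodes, it rests mainly on the Canadian ones.

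**Working it through.** **Plan figure used.** The documents state no AE percentage to reproduce. The only plan figure needed is the denominator: protocol section 3.4 has 50 completers and about 5% dropout, so 50 / 0.95 = 52.6, rounded up to 53. This agrees with the plan.

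**Assumed input.** Canada's share of patients is not given. Protocol section 3.1 names seven cities, three of them Canadian. Equal recruitment by city gives 53 × 3/7 = 23 patients. A range of 20% to 60% gives 53 × 0.20 = 11 and 53 × 0.60 = 32.

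**Formula.** Let c be Canada's share and k the fraction of non-major episodes elsewhere that still reach the eCRF because they are serious or change dosing. Then

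tabulated rate = true rate × [c + (1 − c) × k].

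The worst case is k = 0, when the factor is c. Any k above 0 moves the factor towards 1.

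**Worst-case results for non-major episodes**, with illustrative true rates of 10% on dapagliflozin and 4% on placebo (assumed, not from the documents):

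| Canadian patients | Factor | Dapagliflozin | Placebo | Difference | Ratio |
|---|---|---|---|---|---|
| 11 | 11/53 = 0.21 | 2.1% | 0.8% | 1.2 points | 2.5 |
| 23 | 23/53 = 0.43 | 4.3% | 1.7% | 2.6 points | 2.5 |
| 32 | 32/53 = 0.60 | 6.0% | 2.4% | 3.6 points | 2.5 |

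The true difference is 6.0 points. The ratio does not move because each completing patient takes both treatments under the same site's recording rule, so both arms shrink by about the same factor.

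**Zero count.** The one-sided 95% upper limit with no events is 1 − 0.05^(1/n). For n = 53 it is 5.5%. For n = 23 it is 12.2% (8.9% for n = 32, 23.8% for n = 11). The plan announces no such limit. The comparison shows how far a pooled zero for non-major episodes could be over-read in the worst case.

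**The case against.** The strongest reply has four parts.

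- **The common set is already named.** Protocol section 8.3 says that serious AEs, AEs leading to discontinuation and AEs of special interest are what the study collects. Canada's extra recording follows a national requirement, and pooled tables can be expected to use the common set. This stands for AEs in general. It does not settle hypoglycaemia, because the endpoint itself has no limit to major episodes.
- **No document says all episodes.** The major event is the only one defined, so the endpoint may have been meant that way. That is possible, but none of the four places says so, and one added word would remove the doubt.
- **Other routes exist.** Section 5.4 allows temporary discontinuation for a potential health risk, and an episode handled that way is entered everywhere. Section 8.3 also has some clinically relevant findings reported as AEs with no country limit, and has laboratory results, which include glucose, summarised in the clinical study report for all sites. This stands, and it makes the factors above a worst case.
- **Few episodes are expected.** Sections 1 and 5.4 expect very little hypoglycaemia without diabetes. This largely stands, although section 12.1 lists hypoglycaemia among identified reactions and reports an incidence slightly above placebo with repeated doses up to 100 mg in healthy and type 2 diabetes subjects.

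A reader might go further and infer that every AE outside the common list, such as back pain or polyuria, will be under-reported in pooled tables, or that drug-related AEs cannot be counted. The documents do not support this. No section clearly plans all-patient tables of Canada's extra AEs. The missing AE set, denominator and table shell are details that an analyst would fill sensibly. Section 8.3 already collects a causality rating for serious AEs, discontinuations and events of special interest. Nor do the documents support reading this as a bias in the relative treatment comparison.

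**Conclusion.** The point holds for hypoglycaemia. The endpoint is written without a severity limit, and the recording rule admits non-major episodes from Canada but, with few exceptions, not from the other two countries. Pooled absolute rates and differences for non-major episodes would be too low, at worst cut to Canada's share of patients.

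The direction follows from the text. The size rests on an assumed Canadian share and on no such episodes being captured elsewhere. Major episodes are recorded at every site and are not affected. In practice the effect is likely to be small because few episodes are expected. This is an inexpensive inconsistency to remove and no threat to the trial's main conclusion.

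**What to change.** 1. **Align endpoint and recording.** Choose one, before unblinding:
   - Add all hypoglycaemic episodes, with a written definition, to the events recorded at every site. This costs a small protocol and eCRF amendment. Section 8.3 keeps all AEs in source documents, so past episodes could be transcribed. Notes made without a definition would give uneven ascertainment, and that should be reported.
   - Restate the endpoint as major hypoglycaemic episodes in the protocol Summary, protocol sections 2 and 7.1.3, and SAP section 2.2. This costs a short wording amendment, and milder episodes no longer count towards the endpoint.
2. **SAP section 6.** Base pooled AE tables on the set collected in every country: serious AEs, AEs leading to discontinuation, interruption or dose reduction, and listed events of interest. Show any other AEs for Canadian patients only, with the Canadian denominator, including non-major hypoglycaemia if it is not collected everywhere. This costs a few sentences and one table shell.

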8.2.3 Adverse events of interest

Urinary tract infection or genital infections

All potential events of urinary tract infection or genital infections will be recorded in the eCRF.

Diabetic ketoacidosis (DKA)

All potential events of DKA will be recorded in the eCRF.

Volume depletion

Events of volume depletion (eg, dehydration, hypovolemia, or hypotension) will be collected on the eCRF as AEs.

Fractures

All fractures will be recorded in the eCRF as AEs.

Major hypoglycaemic event

A major hypoglycaemic event is defined as an event that requires assistance of another person to actively administer carbohydrates, glucagon, or take other corrective actions. Plasma glucose concentrations may not be available during an event, but neurological recovery following the corrective actions is considered sufficient evidence that the event was induced by a low plasma glucose concentration. Major hypoglycaemic episodes will be recorded in the eCRF as an AE.

Acute Kidney Injury

Acute kidney injury is defined as an increase of 40% in serum creatinine from the previous visit or hospitalization due to acute kidney injury. All acute kidney injury events will be recorded as an AE.

Amputation and related events:

Amputations and related events will be recorded in the eCRF. Information on the actual amputations will be captured as an AE.

8.3 Recording of Adverse Events

- *Time Period for Collection of Adverse Events*

For this study, SAEs, discontinuations due to AEs (DAEs), and AEs of special interest will be collected from the time of signing the informed consent and throughout the study, including the run-in and wash-out periods. Information about all adverse events (serious or not) will be recorded in source documents (eg, progress notes) according to good clinical practice, and retained at the investigative sites.

- *Follow-up of Unresolved Adverse Events*

Any SAEs, DAEs, or AE of special interest will be followed by the investigator until resolution or until a clinically stable outcome is reached, or until further follow-up is no longer considered by the investigator to provide clinically meaningful information.

- *Variables*

The following variables will be collected for each SAE/DAE/AE of special interest: AE (verbatim).

The date and time when the AE started and stopped.

Intensity.

Whether the AE is serious or not.

Investigator causality rating against the study drug (yes or no).

Action taken with regard to study drug.

AE caused patient's withdrawal from study (yes or no).

Outcome.

In addition, the following variables will be collected for SAEs:

Date AE met criteria for a serious AE.

Date Investigator became aware of the SAE.

AE is serious due to.

- a. Date of hospitalisation (if applicable).
- b. Date of discharge (if applicable).
- c. Probable cause of death (if applicable).

- d. Date of death (if applicable).
- e. Autopsy performed (if applicable).
- f. Causality assessment in relation to Study procedure(s).
- g. Causality assessment in relation to other medication (e.g., concomitant medication, background therapy).

Description of intensity.

The intensity of the reported SAEs/DAEs/AE of interest will be assessed according to the following scale:

- Mild (awareness of sign or symptom, but easily tolerated).
- Moderate (discomfort sufficient to cause interference with normal activities).
- Severe (incapacitating, with inability to perform normal activities).

It is important to distinguish between serious and severe AEs. Severity is a measure of intensity whereas seriousness is defined by the criteria in Section 8.2.2. An AE of severe intensity need not necessarily be considered serious. For example, nausea that persists for several hours may be considered severe nausea, but not a SAE unless it meets the criteria shown in Section 8.2.2. On the other hand, a stroke that results in only a limited degree of disability may be considered a mild stroke but would be a SAE when it satisfies the criteria shown in Section 8.2.2.

- Causality Collection

The Investigator will assess causal relationship between Investigational Product and each SAE/DAE, and answer 'yes' or 'no' to the question 'Do you consider that there is a reasonable possibility that the event may have been caused by the investigational product?'

- *Adverse Events Based on Signs and Symptoms*

All SAEs/DAEs/AE of special interest spontaneously reported by the patient or reported in response to the open question from the study personnel: 'Have you had any health problems since the previous visit/you were last asked?', or revealed by observation will be collected and recorded in the eCRF. When collecting SAEs/DAEs/AEs of special interest, the recording of diagnoses is preferred (when possible) to recording a list of signs and symptoms. However, if a diagnosis is known and there are other signs or symptoms that are not generally part of the diagnosis, the diagnosis and each sign or symptom will be recorded separately.

- ***Adverse Events Based on Examinations and Tests***

The results from protocol mandated laboratory tests and vital signs will be summarised in the clinical study report. Deterioration as compared to baseline in protocol-mandated laboratory values, or vital signs should therefore only be reported as AEs if they fulfil any of the SAE criteria, are the reason for discontinuation of study treatment, or fulfil criteria of AEs of special interest.

If deterioration in a laboratory value/vital sign is associated with clinical signs and symptoms, the sign or symptom will be reported as an SAE/DAE or AE of special interest and the associated laboratory result/vital sign will be considered as additional information. Wherever possible the reporting Investigator uses the clinical, rather than the laboratory term (e.g., anaemia versus low haemoglobin value). In the absence of clinical signs or symptoms, clinically relevant deteriorations in non-mandated parameters should be reported as AE(s).

Any new or aggravated clinically relevant abnormal medical finding at a physical examination as compared with the baseline assessment will be reported as an AE.

8.4 Serious Adverse Event Collecting and Reporting

Following the subject's written consent to participate in the study, all SAEs, whether related or not related to study drug, must be collected, including those thought to be associated with protocol-specified procedures. All SAEs will be collected that occur during the screening period and within 30 days of discontinuing dosing. If applicable, SAEs must be collected that relate to any later protocol-specific procedure (such as follow-up skin biopsy).

The investigator should report any SAE occurring after these time periods that is believed to be related to study drug or protocol-specified procedure.

An SAE report should be completed for any event where doubt exists regarding its status of seriousness.

If the investigator believes that an SAE is not related to study drug, but is potentially related to the conditions of the study (such as withdrawal of previous therapy, or a complication of a study procedure), the relationship should be specified in the narrative section of the SAE Report Form.

SAEs that result in death or are life threatening should be reported expedited to the competent authorities. The expedited reporting will occur not later than 7 days after the responsible investigator has first knowledge of the adverse reaction. This is for a preliminary report with another 8 days for completion of the report. Concurrently, the sponsor's principal investigator and project leader will report SAEs accompanied by a cover page mentioning the study code, patient number, country, investigator, seriousness to AstraZeneca via the e-mail box [contact] within the same timelines.

8.4.1 Suspected unexpected serious adverse reactions (SUSARs)

Adverse reactions are all untoward and unintended responses to an investigational product related to any dose administered.

Unexpected adverse reactions are SUSARs if the following three conditions are met:

1. the event must be serious (see chapter 8.2.2);
2. there must be a certain degree of probability that the event is a harmful and an undesirable reaction to the medicinal product under investigation, regardless of the administered dose;
3. the adverse reaction must be unexpected, that is to say, the nature and severity of the adverse reaction are not in agreement with the product information as recorded in:
 - Summary of Product Characteristics (SPC) for an authorised medicinal product;
 - Investigator's Brochure for an unauthorised medicinal product.

Health Authority and METC Reporting

The sponsor will report expedited the following SUSARs through the web portal *ToetsingOnline* to the METC in the Netherlands or accredited ethics committees in other countries:

- SUSARs that have arisen in the clinical trial that was assessed by the METC;
- SUSARs that have arisen in other clinical trials of the same sponsor and with the same medicinal product, and that could have consequences for the safety of the subjects involved in the clinical trial that was assessed by the METC.

The remaining SUSARs are recorded in an overview list (line-listing) that will be submitted once a year to the METC. This line-listing provides an overview of all

SUSARs from the study medicine, accompanied by a brief report highlighting the main points of concern.

The expedited reporting of SUSARs through the web portal ToetsingOnline is sufficient as notification to the competent authority.

The sponsor will report expedited all SUSARs to the competent authorities in other Member States, according to the requirements of the Member States. Concurrently, sponsor will report SUSARs to AstraZeneca via the e-mail box [contact] within the same timelines.

Sponsor will report SAE expedited SAR to competent authorities in each member state. The expedited reporting will occur not later than 15 days after the sponsor has first knowledge of the adverse reactions. For fatal or life threatening cases the term will be maximal 7 days for a preliminary report with another 8 days for completion of the report. Concurrently, the investigator (sponsor) will report SAEs accompanied by a cover page mentioning the study code, patient number, country, investigator, seriousness to AstraZeneca via the e-mail box

[contact] within the same timelines.

In an emergency, unblinding can be performed in the electronic data capture (EDC) system IBM Clinical Development (eClinicalOS) to identify the treatment given to that subject. Unblinding is not to be performed for any reason, other than an emergency where unblinding is required. When the Investigator unblinds the subject he/she must note the date, time and reason for removing it and record this information in the Comments section of the CRF and in the source data. He/she must also immediately inform the project leader/principal investigator at the UMCG (sponsor) and the site monitor that the on the unblinding of the subject treatment. Even though the subject has been unblinded, any blood samples for safety or pharmacodynamic assessments will continue to be drawn, for at least 24hr following the last dose as long as doing so will not compromise subject welfare.

It is the responsibility of the Principal Investigator to ensure the investigator site staff are appropriately trained on the unblinding procedure in case of emergency. Study drug must be discontinued after unblinding but the subject will be followed until resolution of the adverse event. It is the intent that subjects who discontinue treatment with the study drug will continue in the study according to the visit schedule described in the Time and Events Table. At the conclusion of the study, the occurrence of any unblinding can be reported.

